12.6.3.2 Human Smoking Topography Parameters

The HST assessments will take place on Day 0, Day 1 and Day 4 in the THS 2.2 and CC arms only, if CC are compatible with the HST SODIM® device.

The per puff parameters are shown in **Table 8** and the per cigarette parameters are shown in **Table 9**.

The per-cigarette parameters derived from the HST assessments will be summarized along with their changes from baseline. The per-puff and per-cigarette parameters will be listed. In addition the product mean and 95% CI per cigarette parameters will be presented graphically.

The per-cigarette parameters will be analyzed on Days 1 and 4 separately using an ANCOVA model on the log-transformed HST parameter with terms for log-transformed baseline score, sex, average daily CC consumption over the last 4 weeks as reported during screening, product. No adjustment will be made for multiple comparisons.

The SAS code will be the same as described in Section **12.6.1.1 “Primary Biomarkers of Exposure in 24 hour collection”**.

LS means for each product along with the ratio (THS 2.2 : CC) and 95% CI will be presented in the tables.

All figures, summaries and analyses will be performed on the FAS.

The data will be presented in the below outputs, the TFL number refers to the TFL number in the accompanying TFL shell document:

TFL number	Title
FIGURES	
15.1.2.39	HST per Cigarette Parameters Arithmetic Mean and 95% CI – FAS
TABLES	
15.2.4.59	Descriptive Statistics of HST Parameters per Cigarette – FAS
15.2.4.60	Analysis of HST per Cigarette – FAS
LISTINGS	
15.3.7.1	Listing of HST Assessments

12.6.3.3 Human Smoking Topography Questionnaire

The HST questionnaire will be administered on Days 0 and 4.

The number and percentage of subjects in each category of the items of the questionnaire will be summarized. The individual responses will be listed.

All summaries will be performed on the FAS.

The data will be presented in the below outputs, the TFL number refers to the TFL number in the accompanying TFL shell document:

TFL number	Title
TABLES	
15.2.4.61	Descriptive Statistics of HST Questionnaire Data – FAS
LISTINGS	
15.3.7.2	Listing of HST Questionnaire Results

12.6.3.4 CYP2A6 Activity

CYP2A6 activity will be measured in plasma on Days 0 and 6. In this study the CYP2A6 activity will be calculated using the metabolic ratio of trans 3' hydroxycotinine and cotinine, as described in Section 7.1.5 “CYP2A6”. Descriptive statistics of the values and change on Day 6 from Day 0 and supportive listings will be provided.

The analysis will compare the Day 6 values (both absolute and change from baseline) between the THS 2.2 and CC arms between the THS 2.2 and SA arms. An ANCOVA model will be used with terms for baseline, sex, average daily CC consumption over the last 4 weeks as reported during screening and product. No adjustment will be made for multiple comparisons.

The SAS code will be the same as described in Section 12.6.1.1 “Primary Biomarkers of Exposure in 24 hour collection”.

LS means for each product along with the difference (THS 2.2 - CC) and 95% CI will be presented in the tables

CYP2A6 activity will also be examined to compare the reductions in THS 2.2 vs. SA using the same methodology as above.

The data will be presented in the below outputs, the TFL number refers to the TFL number in the accompanying TFL shell document:

TFL number	Title
TABLES	
15.2.4.52	Descriptive Statistics of CYP2A6 Activity (%) – FAS
15.2.4.53	Analysis of CYP2A6 Activity – FAS
LISTINGS	
15.3.6.15	Listing of CYP2A6 Activity and Changes from Baseline

12.6.3.5 Relationship between BoExp and NEQ

The analysis of the relationship between NEQ and primary and secondary BoExp will be reported in a separate report as stated in Section 9 “Changes from the Protocol Specified Statistical Analysis”.

12.6.3.6 Risk Markers

The risk markers are 8-epi-PGF2 α and 11-DTX-B2 in urine and will be presented as quantity excreted over 24 hours and concentration adjusted for creatinine.

The quantity excreted over 24 hour, percent changes in the quantity excreted and the concentration adjusted for creatinine in 24 hour urine will be listed and summarized. In addition line graphs will be produced for product means (and 95% CI) over all timepoints.

The analysis will compare the concentrations adjusted for creatinine and the quantity excreted over 24 hour on Day 5 between the THS 2.2 and CC arms, and between the THS 2.2 and SA arms. An ANCOVA model will be used with terms for Day 0 concentration adjusted for creatinine or quantity excreted over 24 hours, sex, average daily CC consumption over the last 4 weeks as reported during screening and product. No adjustment will be made for multiple comparisons.

If there is evidence of non-normality (see Section 12.6, “Planned Statistical Analyses” then the concentrations or quantity excreted will be transformed prior to analysis.

The SAS code will be the same as described in Section 12.6.1.1 “Primary Biomarkers of Exposure in 24 hour collection”.

LS means for each product along with the difference (THS 2.2 - CC) and 95% CI will be presented in the tables.

The data will be presented in the below outputs, the TFL number refers to the TFL number in the accompanying TFL shell document:

TFL number	Title
TABLES	
15.2.4.54	Analysis of Urinary 8-epi-PGF2 α on Day 5 – FAS
15.2.4.55	Descriptive Statistics of Urinary 8-epi-PGF2 α – FAS
15.2.4.56	Analysis of Urinary 11-DTX-B2 on Day 5 – FAS
15.2.4.57	Descriptive Statistics of Urinary 11-DTX-B2 – FAS
LISTINGS	
15.3.3.3	Listing of Risk Markers and Collection Times

12.6.3.6.1 Relationship Between Risk Markers, BoExp and NEQ

The relationship between risk markers and BoExp will not be reported as stated in Section 9 “Changes from the Protocol Specified Statistical Analysis”.

The relationship between risk markers, and NEQ will be examined by fitting a general linear model (glm) with terms for baseline and Day 5 NEQ for each treatment arm separately. The SAS code to be used is as shown below:

```
Proc glm data=_data_ ;
  Model Risk marker = baseline NEQ Day 5 NEQ;
  Run;
```

The slope along with 95% CIs and the p-value will be presented for each analysis.

In addition scatterplots of each risk marker separately with NEQ, with the regression from the above model shown on the plot if there was a significant slope from the above model.

In these plots the risk marker will be on the y-axis.

The data will be presented in the below outputs, the TFL number refers to the TFL number in the accompanying TFL shell document:

TFL number	Title
FIGURES	
15.1.2.40	Scatterplot of 8-epi-PGF2 α Urinary Concentration Adjusted for Creatinine vs. NEQ Urinary Concentration Adjusted for Creatinine – FAS
15.1.2.41	Scatterplot of Urinary 8-epi-PGF2 α Quantity Excreted over 24 hours vs. Urinary NEQ Quantity Excreted over 24 hours – FAS
15.1.2.42	Scatterplot of 11-DTX-B2 Urinary Concentration Adjusted for Creatinine vs. NEQ Urinary Concentration Adjusted for Creatinine – FAS
15.1.2.43	Scatterplot of Urinary 11-DTX-B2 Quantity Excreted over 24 hours vs. Urinary NEQ Quantity Excreted over 24 hours – FAS
TABLES	
15.2.4.58	Statistical Analysis of the Relationship Between Risk Markers and NEQ – FAS

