 - THS 2.2 Arm: 80 subjects, ad libitum use of the product.
 - CC Arm: 40 subjects, ad libitum use of their preferred CC brand.
 - SA Arm: 40 subjects who will abstain from smoking.

Subjects will be informed of their randomized study arm by the study site staff on Day 1 prior to 06:30 AM.
- Exposure period (from Day 1, 06:30 AM until Day 5, 11:00 PM):

The exposure period will consist of 5 days of ad libitum use of the assigned product between 06:30 AM and 11:00 PM in THS 2.2 and CC arms. Use of any tobacco/nicotine-containing product other than the assigned product will not be allowed and may, at the discretion of the Investigator or designee, result in the subject withdrawal from the study.

Subjects in the SA arm will be asked to abstain from smoking any nicotine/tobacco-containing product and will not be provided with medication to support SA.

The end of the 24-hour urine collection period for Day 5 will end in the morning on Day 6 prior to Discharge.
- Day of Discharge (Day 6) (from Day 5, 11:01 PM to time of Discharge):

Procedures of Discharge, including but not limited to laboratory parameters, will be conducted to discharge the subject from the clinic after 9 days in a confined setting. Use of CC will be allowed on Day 6, but only after spirometry has been performed.
- Safety follow-up period (from Day 6, time of Discharge to Day 13):

Confidentiality statement: Data and information contained in this document are considered to constitute trade secrets and confidential commercial information, and the legal protections provided to such trade secrets and confidential information are hereby claimed under the applicable provisions of applicable law. No part of this document may be publicly disclosed without the written consent of Philip Morris Products S.A.

After time of Discharge, subject will enter a 7-day safety follow-up during which there will be recording of spontaneously reported new AEs/SAEs and the active follow-up of ongoing AEs/SAEs by the study site. In general, all AEs will be actively followed until resolved, stabilized (i.e., no worsening of the event), or a plausible explanation for the event has been found. The end of study (EOS) is defined as the time of Discharge on Day 6 plus 7-day follow-up period.

During the study, subjects in the CC and THS 2.2 arms who want to quit smoking will receive appropriate medical advice and will be referred to a smoking cessation counselor.

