5.3 Exploratory Objectives and Endpoints

1. To describe the following parameters in smokers switching from CC to THS 2.2 as compared to smokers continuing to smoke CC and smokers switching from CC to SA:

Endpoints:

- Ames Mutagenicity test (YG1024+S9).
- The total score, factor 1 (relief) and factor 2 (reward) from Questionnaire of Smoking Urges (brief version) [QSU-brief] (Cox et al. 2001)
- The total scores from Minnesota Nicotine Withdrawal Scale (MNWS) (Hughes and Hatsukami 2008).

- CYP2A6 enzymatic activity as molar ratio of 3-hydroxycotinine and cotinine
- Selected risk markers (expressed as quantity excreted and concentration adjusted for creatinine) in 24-hour urine:
 - 8-epi-prostaglandine F2 α (8-epi-PGF2 α)
 - 11-dehydro-thromboxane B2 (11-DTX-B2)

2. To evaluate in smokers switching from CC to THS 2.2, and smokers continuing smoking CC and smokers switching from CC to SA the relationship between¹:

Endpoints:

- Primary and secondary BoExp and NEQ:
- NEQ in urine by:

– Blood COHb.	– 2-NA in urine.
– MHBMA in urine.	– o-tol in urine.
– 3-HPMA in urine.	– CEMA in urine.
– S-PMA in urine.	– HEMA in urine.
– Exhaled CO.	– B[a]P in urine.
– 1-OHP in urine.	– HMPMA in urine.
– Total NNN in urine.	– S-BMA in urine.
– 4-ABP in urine.	– Total NNAL in urine.
– 1-NA in urine.	

¹ The reporting of this objective will be the subject of a separate report.

- Selected risk markers and NEQ² :
- NEQ in urine by:
 - 8-epi-PGF2α in urine
 - 11-DTX-B2 in urine

All biomarkers measured in urine will be expressed as quantity excreted and concentration adjusted for creatinine in 24-hour urine.

3. To describe the following parameters over the course of the study in smokers switching from CC to THS 2.2 as compared to smokers continuing smoking CC:

Endpoints:

- The subscales from the Modified Cigarette Evaluation Questionnaire (MCEQ) (Cappelleri et al. 2007).
- The following parameters measured per cigarette from the human smoking topography (HST) device.
 - Total number of puffs.
 - Total puff volume.
 - Average puff volume.
 - Average puff duration.
 - Total puff duration.
 - Average flow.
 - Average Peak flow.
 - Total inter puff interval.
 - Average inter puff interval.
 - Total smoking duration.
 - Total work.
 - Average work.
 - Average pressure drop.
 - Average peak pressure drop.
 - Smoking intensity.
 - Puffing time index.
 - Puff frequency.
 - HST questionnaire.

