7.1.2 Risk Markers

For those risk markers measured in urine an adjustment of the concentration for creatinine in urine will be calculated as:

$$\text{Risk Marker (corrected for creatinine)} = \frac{[\text{Risk Marker}]}{[\text{Creatinine}]}$$

where the concentrations are measured from the same 24 hour urine collection.

The quantity excreted for the risk markers measured in urine over 24 hours will be calculated as:

$$\text{Quantity Excreted over 24 hours} = [\text{Risk Marker}] * \text{urine volume}$$

where the concentration and the urine volume are from the same 24 hour urine collection.

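### The risk marker–NEQ regression has no creatinine term, so either planned urine scale can show a spurious slope and neither is protected in all cases

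*SAP*

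**What the plan says.** For the link of NEQ with the two risk markers (8-epi-PGF2α and 11-DTX-B2), SAP 12.6.3.6.1 states that it "will be examined by fitting a general linear model (glm) with terms for baseline and Day 5 NEQ for each treatment arm separately". In code this is written as "Model Risk marker = baseline NEQ Day 5 NEQ". There is no term for creatinine, sex or body size. The between-arm model for the same markers in SAP 12.6.3.6 does include sex.

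Two scales are planned. SAP 5.3 says for this objective: "All biomarkers measured in urine will be expressed as quantity excreted and concentration adjusted for creatinine in 24-hour urine". The output list in 12.6.3.6.1 pairs the plots accordingly. Figures 15.1.2.40 and 15.1.2.42 use the adjusted scale (for example "Scatterplot of 11-DTX-B2 Urinary Concentration Adjusted for Creatinine vs. NEQ Urinary Concentration Adjusted for Creatinine"), and Figures 15.1.2.41 and 15.1.2.43 use quantity excreted. No rule says which scale prevails if they disagree.

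SAP 7.1.2 defines the adjusted marker as its concentration over creatinine concentration, "where the concentrations are measured from the same 24 hour urine collection". SAP 7.1.3 divides NEQ by creatinine in the same way. Slopes, 95% CIs and p-values are reported, and the fitted line is drawn only when the slope is significant. Under SAP 9 this is the one risk-marker relationship kept for the clinical study report.

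**The concern.** When two variables are divided by the same third variable, they can correlate even if their numerators are unrelated. Here the Day 5 marker and Day 5 NEQ on the adjusted scale both carry the Day 5 creatinine value, and nothing in the model removes it. The mirror-image problem affects quantity excreted: if both amounts rise with body size, or both fall when a collection is incomplete, they move together for reasons unrelated to nicotine exposure.

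What is at stake is how an exploratory result reads. An artefactual slope would come with a p-value and a CI, and because lines are drawn only when significant, it is the slope the plot would show. If the two scales disagree, the reader has no basis in the plan for choosing between them.

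**Working it through.** **Reading of the model.** I take the outcome as the Day 5 risk marker and the slope of interest as Day 5 NEQ; the SAP code does not say either explicitly. The test is two-sided at 5%, the general level in Protocol 12.1.5.

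**Inputs from the documents.** Arm sizes come from Protocol 4.1. The heated-tobacco group has n = 80 ("THS 2.2 Arm: 80 subjects, ad libitum use of the product"). Continuing smokers number 40 ("CC Arm: 40 subjects, ad libitum use of their preferred CC brand"), and the abstinence group is also planned at 40 ("SA Arm: 40 subjects who will abstain from smoking"). So n = 80 or 40 per fit. SAP 8 assumes a 24.71 ng/g creatinine difference (20%) and SD 43.78 for 11-DTX-B2. Reading the 20% as relative to the mean, that mean is 24.71/0.20 = 123.6 and the CV is 43.78/123.6 = 0.354, a log SD of √ln(1 + 0.354²) = 0.34.

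**Assumed, because the documents give no figure.** Log SDs: marker 0.35 (close to the value above), NEQ 0.5, creatinine output s = 0.1 to 0.3. Day 0 to Day 5 correlations: NEQ 0.6, creatinine 0.7.

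**Algebra.** Urine volume cancels in the ratio, so on the log scale the adjusted value is log amount minus C, where C is log 24-hour creatinine output. Let log marker = u + aC and log NEQ = v + aC, with u and v unrelated (no true relationship).

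- Adjusted scale: both variables carry −(1−a)C.
- Quantity scale: both variables carry +aC.

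With k = 1−a (adjusted) or k = a (quantity), the induced log-scale correlation is

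r = k²s² / √[(0.35² + k²s²)(0.5² + k²s²)]

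- k = 1, s = 0.1: 0.01/√(0.1325 × 0.26) = 0.05
- k = 1, s = 0.2: 0.04/√(0.1625 × 0.29) = 0.18
- k = 1, s = 0.3: 0.09/√(0.2125 × 0.34) = 0.33
- k = 0.5, s = 0.3: 0.0225/√(0.145 × 0.2725) = 0.11

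The two scales are symmetric: a = 0 harms the adjusted scale exactly as a = 1 harms quantity, and a = 0.5 harms both a little.

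**Benchmark.** The plan's only figure here is the 5% level. With amounts unrelated to creatinine and not divided by it, simulating the SAP model gave 4.8% to 5.4%.

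**False-positive rate of the Day 5 slope.** SAP model on the untransformed scale, including the baseline NEQ term; 8,000 simulated trials per cell; each entry is n = 80 / n = 40:

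| Truth | s | Adjusted scale | Quantity scale |
|---|---|---|---|
| Amounts unrelated to creatinine output (a = 0) | 0.1 | 7% / 6% | 5% / 5% |
| | 0.2 | 21% / 14% | 5% / 5% |
| | 0.3 | 52% / 32% | 5% / 5% |
| Proportional to its square root (a = 0.5) | 0.1 | 5% / 6% | 5% / 5% |
| | 0.2 | 6% / 6% | 6% / 6% |
| | 0.3 | 12% / 9% | 11% / 9% |
| Fully proportional (a = 1) | 0.1 | 5% / 5% | 7% / 6% |
| | 0.2 | 5% / 5% | 21% / 14% |
| | 0.3 | 4% / 5% | 53% / 31% |

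Monte Carlo error is about one percentage point per cell at most.

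**Sensitivity.** With marker log SD 0.4 and more stable subjects (correlations up to 0.8 for NEQ and 0.9 for creatinine), the wrong-scale rate at s = 0.2 falls to about 11% (n = 80) and 9% (n = 40), because baseline NEQ absorbs part of the artefact. If the adjusted 11-DTX-B2 CV is held at 35% in total, the marker's own variation shrinks as creatinine variation grows. The adjusted scale at a = 0 then reaches 81% (n = 80) and 53% (n = 40) at creatinine CV 30%. At creatinine CV 10% the rate stays about 6% to 8% for NEQ CV 35% to 50%.

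**With creatinine in the model.** A log-scale regression with log Day 5 creatinine excretion added gave 4% to 6% in every row of the table. Adding Day 0 as well gave 4.7% to 5.3% in 30 scenarios with the adjusted CV held at 35%.

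**The case against.** The strongest reply is that the SAP already shows both scales side by side, so a reader can see whether a slope survives without the divisor. Creatinine adjustment is also the trial's own metric (three of the four primary endpoints use it), the objective is exploratory with no success criterion, and the size of the problem depends on SDs that the documents do not contain.

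Most of this stands. The sizes are conditional, the stakes are low, and using the adjusted scale is consistent with the rest of the plan. The paired display does not settle the matter, though. When the scales disagree, the display cannot say whether the divisor created the slope or removed a shared factor, and in the intermediate case both are mildly inflated in the same direction.

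A reader might infer something stronger: that dividing by creatinine necessarily manufactures a slope, and that quantity excreted is therefore the safe analysis of record. The documents do not support that. It requires 24-hour amounts to be unrelated to creatinine output, which neither document states. If they are proportional to it, the adjusted scale holds its level and the quantity scale is biased by the same margin. Nor can the point be carried firmly into the separate report on biomarkers of exposure and NEQ, because that model is not given.

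**Conclusion.** The gap is real but conditional. Without a creatinine term, each planned version of the regression is valid under one assumption about how amounts relate to creatinine output and invalid under the opposite one, and the plan does not say which assumption it makes. With creatinine log SD 0.2 to 0.3 and the other assumed values above, the wrong scale rejects in roughly 13% to 52% of null trials. The intermediate case gives roughly 5% to 12% on both scales, and log SD 0.1 only about 6% to 8%. These are illustrations over assumed SDs and correlations, not estimates for this trial. The point concerns an exploratory result; the primary endpoints and success criterion are untouched. It is worth changing because the remedy is cheap and alters slopes, p-values and fitted lines that the report will show.

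**What to change.** In SAP 12.6.3.6.1, fit the risk marker–NEQ model within arm on the log scale with log 24-hour creatinine excretion (creatinine concentration × urine volume) as a covariate, and name that slope the main result. Use Day 5 creatinine, and preferably Day 0 as well. With both in the model, the log-adjusted and log-quantity fits are reparameterisations of each other and give the same NEQ slopes, so the choice of scale stops mattering.

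Keep the two planned scales as supportive, and do not promote quantity excreted alone. Add a note under the creatinine-adjusted scatterplots that both axes share a creatinine divisor.

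The cost is one or two degrees of freedom per arm and a slope read on the log scale. Creatinine and urine volume are already measured for every 24-hour collection, and values below the quantification limit are already set to half that limit (SAP 7.1), so logs can be taken.

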12.6.3.7 Ames Mutagenicity Test

The 24 hour urine collection for the Ames mutagenicity test will be on Day 0 and Day 5.

Descriptive statistics of the values and change on Day 5 from Day 0 of the YG1024+S9 mutagenicity will be provided, along with listings.

The data will be presented in the below outputs, the TFL number refers to the TFL number in the accompanying TFL shell document:

TFL number	Title
TABLES	
15.2.4.43	Descriptive Statistics of Ames Mutagenicity Test (YG1024+S9) (units – FAS)
LISTINGS	
15.3.5.1	Listing of Mutagenicity Results and Changes from Baseline

12.6.3.8 Visual Inspection of the Tobacco Plugs

The collection of the tobacco plugs from the THS 2.2 products will be performed on Days 1 to 5. The number and percentage of tobacco plugs showing each of the following criteria will be summarized by day: Ashes not anymore visible when shooting picture; No tobacco in plug; Not enough tobacco in the plug to perform the analysis; Tobacco plug destroyed, analysis impossible; No tobacco plug in the vial; Other error.

The data will be presented in the below outputs, the TFL number refers to the TFL number in the accompanying TFL shell document:

TFL number	Title
TABLES	
15.2.4.62	Descriptive Statistics of Visual Inspection of the THS 2.2 Tobacco Plugs Data – FAS
LISTINGS	
15.3.6.16	Listing of Visual Inspection of the Tobacco Plugs Results

12.6.3.9 Filter Analysis

The filter analysis from the THS 2.2 products will be performed from Days 1 to 5. Descriptive statistics will be provided for smoke nicotine in filter and UV absorbance at 310 nm along with listings.

The data will be presented in the below outputs, the TFL number refers to the TFL number in the accompanying TFL shell document:

TFL number	Title
TABLES	
15.2.4.63	Descriptive Statistics of Filter Analysis from the THS 2.2 Products – FAS
LISTINGS	
15.3.6.17	Listing of Filter Analysis Data

12.6.4 Safety Evaluation

Safety variables monitored in this study include: AEs; vital signs (systolic and diastolic blood pressure, pulse rate, respiratory rate); spirometry; ECG data; concomitant medication, clinical chemistry, hematology, urine analysis safety panel, BMI, physical examination, respiratory symptoms (cough assessment).

The primary analysis of Safety parameters will be conducted on the Safety Population as described in Section 12.1.3 “Descriptive Statistics”.

